Kitelock™, 4% tetrasodium EDTA catheter lock solution is the sole product of SterileCare Inc, a private medical devices and equipment company registered federally in Canada, and based in Markham, Ontario. Kitelock™ is licensed as a medical device, class 2 (license #96962, issue date 2016-05-10), by Health Canada.

RESEARCH DESIGN AND METHODS

The primary objective of this study is to evaluate patient acceptability of tetrasodium EDTA catheter lock solution in home parenteral nutrition patients.

The secondary aims are to evaluate: side effects, time for preparation and injection, cost and patient satisfaction.

This is a prospective, open-label, single-center study of the patient acceptability of using tetrasodium EDTA catheter lock solution in home parenteral nutrition patients. At study baseline, all patients will be on normal saline/heparin lock solution (which they receive normally as current standard of care) for at least 1 month before starting the study, as per inclusion criteria.

Patients will then start with one month (30 days) of their usual heparin and saline flush followed by one month (30 days) of tetrasodium EDTA solution with withdrawal (when possible), followed by one month (30 days) of tetrasodium EDTA solution. During the last week of each of the aforementioned three months, the patients will be asked to evaluate the lock and flush. Patients will be followed and treated according to usual care during the study, except for the catheter lock solution.

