All patients receiving HPN at Toronto General Hospital will be invited to participate in the study. Patients will be recruited at their usually scheduled HPN appointment or by telephone. Consent will be taken by clinical fellow and nurse coordinator. Patients will be instructed on the use of the new lock solution via (1) telephone by the home TPN nurse. The patient or the other person administering the lock solution (usually caregiver or community nurse) will be responsible for filling the provided survey three times: once at the end of each month. The patients will be responsible for filling a data collection form with time of procedure, and any symptoms or side effects as they occur. The patient will receive four phone calls from the home TPN nurse in regards to this study: once at the beginning of the study and once at the end of each month. At each phone visit, the nurse will record the time to perform and any symptoms or side effects that the patient has written down in their data collection form, and administer the survey, in addition to inquiring about any interim events such as hospitalization, surgery and illness (at phone calls

2, 3 and 4) and compliance. The catheter lock solution will be distributed by Ontario Medical Supply, with home TPN solution and supplies, as per the patient's usual delivery schedule. Regular home TPN monitoring labs will be drawn at least once at the beginning of the study and once at the end of the study (3 months later), or more frequently, as clinically indicated or as per the patient's usual care.

SAMPLE SIZE

This is a pilot study; we plan to recruit 20 participants.

INCLUSION CRITERIA

Subjects who meet all of the following criteria can be enrolled in this study:

- Adult over the age of 18
- Both males and females
- Clinically stable for at least 4 weeks with no acute medical co-morbidities

EXCLUSION CRITERIA

- Inability to give informed consent
- Alcohol or drug abuse
- Pregnant and lactating women
- Clinical instability such as the following:
 - Acute pulmonary edema
 - Decompensated heart failure
 - Decompensated chronic liver disease
 - Severe post-traumatic conditions
 - Uncontrolled diabetes mellitus
 - Acute myocardial infarction
 - Acute stroke
 - Acute thromboembolism
 - Metabolic acidosis
 - Sepsis
 - Hypotonic dehydration
 - Coagulopathy with prolonged aPTT or INR
 - Unstable oncology patient
- Subjects who are hypersensitive or allergic to the product ingredients of tetrasodium EDTA

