If flushing Tetrasodium EDTA lock solution through the catheter, repeat above steps but omit 5 - 7.

Cost analysis (this is an estimate which may be modified after the trial):

Type	Solution	Dispensing fee	SAP application	Distribution	Supplies*	Education
Saline/heparin	\$2/use	0	N/A	0/contract	0/contract	0
Tetrasodium EDTA	\$3.50/use	0	N/A	0/contract	10ml syringe without needle	0.5h (\$40/hr)
Saline/taurolidine	\$20/10ml	\$11,99	2h (\$55/h) Per patient		3-5ml syringe with needle	0.5h (\$40/hr)

Measures:

1. Patient acceptability

See Form 2 below

2. Patient satisfaction

See Form 2 below

3. Time to prepare tetrasodium EDTA catheter lock solution

(1) From starting to prepare to infuse TPN to starting the TPN infusion (form 1)

(2) From disconnecting TPN tubing to completing catheter lock solution (form 1)

4. Symptoms and side effects

See Form 1: patient data collection form

5. Labs

Regular TPN labs, as per usual care, at the beginning and end of the study (form 4)

(1) Within 30 days of starting the study

(2) On, or up to 10 days after the last day of using the tetrasodium EDTA lock solution

Data collection forms:

-Form 1: patient data collection form:

-Record symptoms and side effects as they occur

-Record the time of the procedure on the first and last Monday of each 30-day period

-Form 2: survey on ease of use (3 per patient)

- to be filled by person administering the lock (RN, patient, family member), where possible

- to be filled three times, during the phone visit at the end of each month

- Form 3: Education time

-Nurse: over the phone

-Patient demonstration

Clinic Visits:

Clinic visits: None required

Follow up Phone call:

Each phone call will last for around 40 minutes. All participants will receive phone call at baseline and at the end of month 1,2 and 3.

Phone visits:

- (1) At baseline, prior to initiation of the product
- (2) At the end of month 1 (on days 27 to 30)
- (3) At the end of month 2 (on days 57 to 60)
- (4) At the end of month 3 (on days 87 to 90)

Follow-up phone call for the following purpose:

- **Safety:** by asking questions about side effects and tolerance to tetrasodium EDTA solution (from patient data collection form)
- **Compliance:** Recording the number of catheter lock solutions used.
- **Record times of procedure** (from patient data collection form)
- **Record events** (hospitalizations, antibiotics used, or interruption of lock solution use)

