Subject compliance will be checked when they will receive a phone call every months as a follow-up asking about the number of catheter lock solution used and the amount of solution infused. In addition, they will be asked if they have taken the TPN as per the instructions provided to them about the infusion.

SAFETY EVALUATION:

All AEs will be reported and evaluated. The research team will be responsible for detecting and documenting any AE or serious adverse event (SAE). This will help in identifying any untoward medical occurrence, thereby allowing the continuous safety of study subject and provide a greater understanding of the overall safety profile of the investigational product.

Adverse event Definition

An AE is defined as any untoward medical occurrence in a clinical investigation subject administered medical/ pharmaceutical product. An adverse event does not necessarily have to have a causal relationship with the medical/ pharmaceutical product.

An AE can therefore be any unfavorable and unintended sign (including a clinical significant abnormal laboratory finding), symptom, or disease temporally associated with the use of a medicinal product (investigational or marketed), whether or not considered related to treatment with the medicinal product.

An AE includes:

- An exacerbation of a pre existing illness, sign, symptom, or clinical significant laboratory test abnormality as determined by the investigator.
- An illness, sign, symptom, or clinically significant laboratory abnormality that is detected or diagnosed after study drug administration.
- Pre or post treatment events that occur as a result of protocol mandated procedures

An AE does not include:

- Expected worsening of the disease or disorder being studied or signs and symptoms associated with the disease or disorder
- A preexisting disease or condition, present at the start of the study that did not worsen
- Any overdose of the study drug or concurrent medication without any clinical sign or symptom.

Procedure for reporting adverse events

Any sign (e.g., a clinically significant abnormal laboratory finding, as determined by the investigator), symptom or disease described by the subject or noted by the research team will be recorded as an AE. If known, the diagnosis of the underlying illness or disorder will be recorded rather than its individual symptoms.

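### Side-effect questions at the calls and relatedness of adverse events refer to tetrasodium EDTA only, so like-for-like tolerance data from the heparin month are not assured

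*Protocol*

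**What the plan says.** Under Research Design and Methods, each participant has "one month (30 days) of their usual heparin and saline flush", then "one month (30 days) of tetrasodium EDTA solution with withdrawal (when possible"), then a further 30 days of EDTA flushed through. Side effects are a stated secondary aim: "The secondary aims are to evaluate: side effects, time for preparation and injection, cost and patient satisfaction".

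**Wording tied to EDTA**
- Follow-up phone call, Safety: "by asking questions about side effects and tolerance to tetrasodium EDTA solution (from patient data collection form").
- Procedures in case of an adverse event, step 1: the HPN team judges whether the event is related to EDTA. No other lock is named.
- Subject Withdrawal Criteria: the four-week follow-up of unresolved events is counted from stopping EDTA, with longer follow-up at the investigator's judgement.

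**Wording tied to an undefined term**
- One item in the list of what an AE includes covers findings "detected or diagnosed after study drug administration". The relationship item and the SAE window also rest on *study drug*. The protocol never says whether that means EDTA alone or either lock.

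**Neutral wording**
- Research Design and Methods: at each call the nurse records "any symptoms or side effects that the patient has written down in their data collection form", and at calls 2, 3 and 4 also asks about intervening illness, operations and hospital stays.
- Data collection forms: Form 1 takes symptoms as they arise, names no lock, and has timing entries in every 30-day period.
- Safety Evaluation: the core AE definition covers products on trial or already marketed, with no causal link needed. New AEs are recorded at each call.

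**The concern.** Call 2 falls "At the end of month 1 (on days 27 to 30"), at the close of the heparin month. Read literally, the safety purpose has the nurse ask then about tolerance to a product that the participant has not yet received. No matching question about tolerance to heparin is written anywhere. If a symptom does reach the form, the team is told to judge whether EDTA caused it, not whether the heparin lock did.

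The protocol itself warns that patients on parenteral nutrition often have events that come from the nutrition or the underlying disease. All participants take the locks in the same order and there is no parallel group, so month 1 is the only background reference inside the study. If tolerance is asked about or attributed differently in that month, a side-effect count from the two EDTA months is harder to interpret. An answer that was never sought cannot be recovered at analysis, so this has to be settled in the protocol and its forms.

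**Working it through.** The protocol gives no side-effect rate, and its sample size has no derivation ("This is a pilot study; we plan to recruit 20 participants"), so there is no stated figure to reproduce. The check is to set the provisions side by side and ask which of them work in the heparin month.

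| Item | Heparin month (call 2) | EDTA months (calls 3 and 4) |
|---|---|---|
| Form 1 symptoms as they arise | Yes | Yes |
| Nurse records the form entries | Yes | Yes |
| Nurse asks about illness, operations, hospital stays | Yes | Yes |
| Core AE definition and recording of new AEs | Yes | Yes |
| Tolerance question about the lock in use | Not written | Yes |
| Relatedness to the lock in use | Not written | Yes |
| Items resting on *study drug* | Unclear, term undefined | Yes |

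**Step 1: what can be estimated.** Planned exposure with full retention:
- heparin: 20 × 30 = 600 patient-days
- EDTA: 20 × 60 = 1200 patient-days, or 600 for each EDTA method

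The first four rows apply throughout, so an all-cause symptom or AE rate per 30 days can be formed for heparin and for each EDTA method.

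**Step 2: what cannot be estimated on the same footing.** The last three rows differ. A rate of lock-related events can be formed only for EDTA, because relatedness to heparin is never judged. A rate that depends on prompted tolerance questions has no assured counterpart in month 1.

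**Step 3: size.** The documents give no basis for a figure. To show only how the effect would scale, let r be a true monthly symptom rate that is equal in all periods and fully captured on EDTA, and let c be the fraction captured in the heparin month. The apparent excess on EDTA is r − rc = r(1 − c). With assumed values r = 30% and c from 50% to 100%:
- c = 100%: 30% − 30% = 0 points
- c = 50%: 30% − 15% = 15 points, or 0.15 × 20 = 3 participants

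Neither r nor c comes from the protocol. The neutral rows of the table argue for c near the upper end, and c = 100% is quite possible.

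**The case against.** The best reply is that the Safety line describes the nurse going through Form 1, since it ends by naming that form as its source. Form 1 is neutral and in use in every month, so there would be no separate EDTA questionnaire. The words can also be parsed as side effects in general plus tolerance to EDTA. On either reading, month 1 is questioned much as the later months are. In addition, the secondary aim is only to evaluate side effects. The Statistical analysis section lists acceptability, satisfaction and ease of use for comparison with heparin, and does not list side effects.

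Much of this stands, and it rules out several stronger readings that a reader might infer:
- **That the AE definitions are tied to EDTA.** The core definition and the recording rule are product-neutral. An inclusive list with one item on *study drug* does not narrow them.
- **That prompted questioning happens only in the EDTA months.** Call 2 has explicit questions about illness, operations and hospital stays.
- **That the heparin month yields no side-effect rate.** An all-cause rate is available.
- **That EDTA will look worse by some stated amount.** No capture rate appears in the documents.

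The reply does not remove the EDTA-only relatedness step, which does not depend on how the Safety line is parsed. Nor does it supply a tolerance question for heparin. The wording lets two nurses run call 2 differently, and both would be following the protocol.

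**Conclusion.** The point holds as an internal inconsistency of minor severity. The safety purpose of the calls and the relatedness step name EDTA only, while the forms, the call recording and the core AE definition are neutral. All-cause rates by month are secure. Prompted tolerance data and lock-related attribution are not assured for heparin, so the EDTA side-effect rate may lack a like-for-like reference.

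Bias is possible but not shown, and its size is unknown. The 0 to 15 points in the working rest wholly on assumed inputs and are not an estimate. The conclusion assumes that the forms and call scripts add nothing to the wording in the protocol. If the actual call script already asks the same questions about whichever lock was used, only the relatedness step and the undefined term remain.

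**What to change.** 1. Follow-up phone call, Safety: replace the reference to EDTA with *side effects and tolerance to the lock solution used in the month just ended*, and use the same questions at calls 2, 3 and 4.
2. Procedures in case of an adverse event: record relatedness against the lock in use when the event began.
3. Safety Evaluation: define *study drug*, or replace it with a term that covers both locks, so that AE and SAE recording clearly runs from day 1 of the heparin month. Reconcile the starting point for follow-up after withdrawal with the AE section, which counts from the last dose of any catheter lock solution. A participant who leaves in month 1 has no date of stopping EDTA.
4. Tabulate side effects by month and lock, all-cause and lock-related, as description only.

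The cost is a few changes of wording and perhaps one more field on the AE record. The calls are already planned at around 40 minutes each, so the added time is small, and the only other consequence is that a few more events may be recorded in month 1. The change needs to be in place before the first participant's call 2, since answers not sought then cannot be added afterwards.

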At each phone call, new AEs will be recorded on the CRF. The AE term should note the diagnosis of the event, not the individual signs of symptoms (e.g., sneezing, coughing recoded as upper respiratory tract infection).

Also, recorded are

- Start and stop date and time
- frequency (intermittent, continuous)
- Intensity (mild, moderate, severe)
 - Mild: usually transient, requiring no special treatment and generally not interfering with usual daily activities
 - Moderate: usually ameliorated by simple therapeutic maneuvers and impairs usual activities.
 - Severe: requires vigorous therapeutic intervention and or interrupts usual activities. Hospitalization may or may not be required.
- Relationship to study drug (not related, related). An event related to drug treatment, i.e., associated with drug treatment, is considered an adverse drug reaction (ADR). The term related includes unlikely (improbable), possibly, probably, and definitely.
- Whether or not the AE is serious (i.e., an SAE). If identified as an SAE, the AE should be reported on the SAE form and reporting guidelines followed.
- Actions taken (none; study drug dose interrupted or discontinued, other medication change, non drug therapy)
- Outcome (resolved, ongoing, fatal). If the AE has increased in severity or frequency, it should be identified as a new AE and given a new number

AE not resolved at the end of treatment will be followed for up to 4 weeks after the last dose of catheter lock solution or as long as judged medically relevant by the investigator.

Serious Adverse Events

An event that is serious must be recorded on the SAE report form and requires expeditious handling to comply with regulatory requirements.

Serious Adverse Event Definition

An adverse event is considered serious if it

- Occurs during study treatment or within 30 days of last dose of study drug (or after 30 days if considered to be a result of delayed toxicity due to administrations of study drug) and meets any of the criteria outlined below.

An SAE is any AE occurring at any dose that results in any of the following outcomes

- Death
- life threatening. A life threatening AE is any AE that place the subject in the investigator's opinion at immediate risk of death from the reaction as it occurred. It does not include a reaction that, had it occurred in a more serious form, might have caused death.
- Persistent or significant disability or incapacity
- Hospitalization or prolongation of existing hospitalization

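### SAEs count for 30 days after the last EDTA dose, but no scheduled enquiry about new SAEs takes place after the call on days 87 to 90

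*Protocol*

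**What the plan says.** The Research Design and Methods section fixes the sequence: "Patients will then start with one month (30 days) of their usual heparin and saline flush followed by one month (30 days) of tetrasodium EDTA" (lock and withdraw), and then a second 30-day EDTA month. The Lock procedures describe this second month as flush-through.

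Under Serious Adverse Event Definition, an event qualifies if it "Occurs during study treatment or within 30 days of last dose of study drug", or later if attributed to delayed toxicity, and meets one of the listed criteria. Hospitalization is among them.

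The section on reporting adverse events gives the capture step: "At each phone call, new AEs will be recorded on the CRF". Four calls are planned. The last is listed under Phone visits: "At the end of month 3 (on days 87 to 90". In-person contact for the study is excluded: "Clinic visits: None required".

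Three provisions can reach beyond the last call:

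- **Open events.** "AE not resolved at the end of treatment will be followed for up to 4 weeks after the last dose of catheter lock solution", or longer if the investigator judges it relevant. Subject Withdrawal Criteria has a parallel rule for early withdrawals.
- **Laboratory tests.** Measures, item 5, allows the closing draw on the last EDTA day or up to 10 days later.
- **General duty.** Safety Evaluation makes the research team responsible for detecting and documenting AEs and SAEs, and events that the team notes are to be recorded.

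**The concern.** The definition of an SAE and the schedule for finding SAEs end at different times. The definition runs about a month past the end of EDTA, while the last occasion on which anyone is scheduled to ask about new events can fall before EDTA ends. Follow-up of open events does not bridge this, because it applies only to events already known.

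The events most likely to be affected are those the protocol itself treats as typical. The Background names bloodstream infection as the most frequent cause of hospitalization on home PN, and hospitalization makes an event serious. An infection that begins late in the flush-through month and leads to admission after call 4 lies inside the SAE window but outside every scheduled enquiry. Side effects are a secondary aim, and the Background states that no known study has examined this lock in home PN patients. A reader of the safety results would therefore take the 30-day window at face value.

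**Working it through.** The protocol states no coverage figure, so there is none to reproduce. The check is day arithmetic for a patient who completes all three 30-day periods without interruption.

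**Inputs**

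- Heparin on days 1–30, EDTA on days 31–60 and 61–90 (Research Design and Methods).
- SAE window: 30 days after the last dose (Serious Adverse Event Definition).
- Last call: days 87 to 90 (Phone visits).
- Follow-up of unresolved events: 4 weeks, taken as 28 days.
- Closing laboratory draw: up to 10 days after the last EDTA day (Measures).
- 20 participants (Sample Size).

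**EDTA risk window**

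- EDTA days: 90 − 31 + 1 = 60.
- Risk window: 60 + 30 = 90 days, ending on day 90 + 30 = 120.

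**Days with no scheduled enquiry about new SAEs** = 120 − day of last call

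| Last call | Days without enquiry | Share of 90 | EDTA treatment days among them |
|---|---|---|---|
| Day 90 | 30 | 33.3% | 0 |
| Day 89 | 31 | 34.4% | 1 |
| Day 88 | 32 | 35.6% | 2 |
| Day 87 | 33 | 36.7% | 3 |

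If all 20 complete, this is 20 × 30 = 600 to 20 × 33 = 660 of 20 × 90 = 1,800 patient-days.

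**Other readings**

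- If the laboratory draw counted as an enquiry and fell as late as allowed, day 100: (120 − 100)/90 = 22.2%. If it fell on day 90, the share stays at 33.3%.
- If the denominator were days 1–120, heparin month included: 30/120 = 25.0% to 33/120 = 27.5%.

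**Follow-up of open events.** It ends at day 90 + 28 = 118 unless extended, 2 days before the SAE window closes.

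**Illustration only.** The documents give no SAE rate. For an assumed per-patient risk *p* of a new SAE in 30 days, the expected number of patients among 20 with one is 20*p*, and the chance of at least one is 1 − (1 − *p*)^20.

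| Assumed *p* | Expected number | Chance of at least one |
|---|---|---|
| 2% | 0.4 | 33% |
| 5% | 1.0 | 64% |
| 10% | 2.0 | 88% |

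These are events that could occur in the 30 days, not events that would necessarily be missed.

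**The case against.** A reader might infer that nothing is observed after call 4. The documents do not support that. The laboratory draw can fall as late as day 100, and Safety Evaluation counts a clinically significant laboratory abnormality as an AE. The duty to detect and document SAEs is not confined to phone calls. The study also runs at one centre inside the patients' own HPN programme, whose nurse makes the calls and whose team handles line infections. That team would plausibly hear of many late infections and admissions.

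It can also be said that the 30-day phrase only defines which events count and promises no contact on day 120. Its delayed-toxicity clause is open-ended, so no fixed call could cover it fully. A further stronger inference is that a reported EDTA SAE count is shown to be biased low. The Statistical analysis section specifies no SAE count, rate or comparison, and patient-days without a call are not missed events.

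Most of this stands and limits the claim. It does not remove the mismatch. A blood draw does not ask about hospitalization. The general duty comes with no method for the period after call 4, whereas the method that is described stops by day 90. Reliance on spontaneous reports or chance discovery in usual care differs from the systematic questioning used up to call 4.

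**Conclusion.** The point holds as a mismatch between the SAE definition and the contact schedule. Roughly a third of each completer's EDTA risk window has no scheduled ascertainment of new SAEs, and up to 3 of those days are treatment days. The figure assumes consecutive 30-day periods, a last EDTA lock on day 90, and that the laboratory draw is not an enquiry about events. The patient-day total further assumes that nobody drops out.

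The likely direction is under-counting of late SAEs in the safety data. Its size cannot be determined from the documents, since it depends on the SAE rate and on how many late events usual care brings to light. Early withdrawals have a similar gap: AEs are sought when they leave, after which only unresolved ones are followed. The primary outcome, the proportion willing to continue the lock, does not depend on any of this.

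**What to change.** 1. Add one ascertainment step at least 30 days after each patient's last EDTA lock. It can be a review of the HPN programme record or the next routine HPN contact. Record any SAE or hospitalization since call 4, including on any EDTA days after that call.
2. Apply the same step to early withdrawals, counted from their own last EDTA lock.
3. Reconcile the 4-week follow-up of unresolved AEs with the 30-day SAE window, so that the two passages do not imply different end dates.

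The cost is about 20 short checks by the existing HPN team, with no added study clinic visit or procedure. Final safety data would be available about one month later; the acceptability analysis need not wait for them.

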- Congenital anomaly/ birth defect
- Important medical events that may not result in death, be life threatening, or require hospitalization may be considered an SAE when, based upon appropriate medical judgment, they may jeopardize the subject or may require medical or surgical intervention to prevent 1 of the other outcome listed in this definition.

Data storage:

All data regarding the study will be stored in hospital file and UHN computer system of the clinical fellow, nurse coordinator and principal investigator for 10 years.

Statistical analysis:

Simple statistics such as mean, median and frequency will be used to initially assess the data as follows:

1. Patient acceptability will be analyzed as the proportion of participants willing to continue use of the catheter lock solution. The solution will be deemed acceptable if at least 75% of participants are willing to continue use of the solution.

2. Patient satisfaction will be analyzed as the proportion of participants overall satisfied with the catheter lock solution.

3. Ease of use will be analyzed as the proportion of participants answering that the process is easy or very easy. This will be calculated by taking the average of the answers to the 3-5 questions at the top of the questionnaire addressing the ease of the procedure (preparation of the solution, instilling, withdrawing etc). Each step will also be analyzed individually (averaged over all of the patients), to determine if one of these individual averages falls below 3 (suggesting that that procedure is difficult).

The means of patient acceptability, patient satisfaction and ease of use of the new catheter lock solution flush and the new catheter lock solution withdraw will each be compared, separately, to those of the heparin group and to each other using the chi squared test to determine if there is any difference between them.

Sample Size and Feasibility

This is a pilot study; we plan to recruit 20 participants.

Limitations:

- The expected sample size is 20 subjects and some of them live far away from TGH. This can be avoided a phone call follow-up every month.
- Some of the patients may not be compliant with the catheter lock solution or TPN infusion. Compliance will be checked by counting the number of catheter lock solutions and tpn bags delivered and used. However, compliance cannot be predicted.

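### Ease of use is scored on a graded scale but compared between locks as a yes/no proportion, which under plausible assumptions costs about 20 to 40 points of power in a 20-patient paired study

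*Protocol*

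**What the plan says.** All of this is in the Protocol, mostly under Statistical analysis.

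- **Outcome.** Item 3: "Ease of use will be analyzed as the proportion of participants answering that the process is easy or very easy".
- **Derivation.** The next sentence builds it from a graded score: "This will be calculated by taking the average of the answers to the 3-5 questions at the top of the questionnaire". The steps named as examples are preparing, instilling and withdrawing.
- **Descriptive use of the grades.** Each step is also averaged over patients, "to determine if one of these individual averages falls below 3 (suggesting that that procedure is difficult").
- **Comparison.** The closing paragraph begins "The means of patient acceptability, patient satisfaction and ease of use of the new catheter lock solution flush" and goes on to the withdraw procedure. Each is compared "to those of the heparin group and to each other using the chi squared test".
- **Design.** The same patients use all three lock procedures in turn, and the survey (Form 2) is "to be filled three times, during the phone visit at the end of each month".
- **Size.** "This is a pilot study; we plan to recruit 20 participants". Subject Withdrawal Criteria adds that those who leave are not replaced, so 20 is the most pairs there can be.

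No significance level, effect size, standard deviation, correlation or power is stated. Form 2 is not shown.

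**The concern.** A graded score is computed for each patient and each lock, but the only between-lock comparison uses whether the patient falls on one side of a cut. A patient who moves from 'very easy' on heparin to 'easy' on EDTA counts as unchanged, and so does one who moves from 'difficult' to 'very difficult'. The Protocol gives no reason for preferring the cut to the score when locks are compared.

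Ease of use is in the study title, and the Significance section gives it as a reason why EDTA may replace heparin. With at most 20 pairs, a real difference in ease could often be missed, and a non-significant result could then be read as equal ease. Pairing the binary test and fixing its cut-off would not by itself recover the information lost.

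**Working it through.** There is no power figure in the plan to reproduce. The inputs are as follows.

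- From the Protocol: 20 patients, each rating all locks; 3 to 5 graded items averaged; 3 used as the threshold for a difficult step.
- Assumed: two-sided 0.05; items scored 1 to 5; 'easy or very easy' meaning an average at or above a cut near 4; effect sizes, heparin baseline and correlations as stated below.

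**Step 1: what the binary test needs.** With m patients crossing the cut, all in one direction, the exact McNemar p-value is 2 × 0.5^m. For m = 5 it is 0.0625, and for m = 6 it is 0.031. At least 6 of the 20 patients must cross the cut, with none crossing back, before this test can reach 0.05. Movement on one side of the cut adds nothing.

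**Step 2: a check that can be redone by hand.** Treat the score as bivariate normal with correlation ρ between locks, heparin proportion 'easy' p1 and standardised paired difference d. The EDTA proportion is p2 = Φ(Φ⁻¹(p1) − d√(2(1−ρ))). With p1 = 0.80 and ρ = 0.3:

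- d = 0.5: p2 = Φ(0.842 − 0.5 × 1.183) = Φ(0.250) = 0.60
- d = 0.8: p2 = Φ(0.842 − 0.8 × 1.183) = Φ(−0.105) = 0.46

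The paired t-test has noncentrality d√20. McNemar power follows from the two discordant probabilities of the bivariate normal, summed over all outcomes for 20 pairs.

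| d | 'Easy', heparin vs EDTA | Paired t | McNemar exact | mid-p | asymptotic | Loss (points) |
|---|---|---|---|---|---|---|
| 0.5 | 80% vs 60% | 56% | 18% | 28% | 30% | 38 / 29 / 27 |
| 0.8 | 80% vs 46% | 92% | 54% | 65% | 66% | 39 / 27 / 26 |

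At d = 0.5, with p1 from 0.7 to 0.8 and ρ from 0.3 to 0.7, the loss is 34–50 points (exact), 25–43 (mid-p) and 24–36 (asymptotic).

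**Step 3: simulation with ordinal items.** Items are cut from a latent normal to a 1–5 scale and averaged. The cut is a mean of 4 or more, the patient share of variance is 0.2 or 0.4, and each setting has 2,000 trials. Chi-squared here is the uncorrected, unpaired test. Ranges run over the two variance shares.

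| Items | Shift (latent SD) | McNemar exact | Chi-squared | Signed-rank |
|---|---|---|---|---|
| 3 | 0.5 | 20–23% | 25–32% | 56–62% |
| 3 | 0.8 | 59–62% | 62–70% | 92–96% |
| 4 | 0.5 | 22–26% | 26–35% | 64–66% |
| 4 | 0.8 | 62–69% | 62–75% | 97% |
| 1 | 0.5 | 10% | 17–20% | 31–39% |
| 1 | 0.8 | 32% | 44–47% | 69–76% |

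Over the better binary test, setting by setting, the signed-rank gain is 22–37 points with 3 items (for example 56 − 32 = 24 and 62 − 25 = 37), 22–40 with 4 items and 11–32 with a single item. The signed-rank test rejected in 4–5% of trials under no difference.

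**Step 4: how far the figure depends on the assumptions.** A grid of 1,512 scenarios varied the number of items (3–5), baseline, shift, correlations and cut (3.5 or 4.0). Median losses with a correctly paired binary test were:

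| Power of signed-rank on the score | Exact | mid-p | Asymptotic |
|---|---|---|---|
| Below 30% | 15 | 12 | 9 |
| 30–50% | 31 | 24 | 20 |
| 50–80% | 44 | 32 | 28 |
| 80–95% | 46 | 33 | 30 |
| 95% or more | 17 | 10 | 9 |

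Part of the exact-test loss is that test's conservatism. The asymptotic column shows what remains without it. Individual scenarios run from near 0 (very large effects) to over 60 points (ceiling, high correlation).

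**Step 5: which steps to average.** The HPN administration section says EDTA needs extra instruction because it is drawn up from a vial and withdrawn, whereas heparin comes pre-filled. Suppose EDTA is harder only in those added steps. A signed-rank test restricted to steps common to both locks then has about 5% power, no more than its error rate. The planned all-step binary outcome (exact McNemar) has 30–54%, and signed-rank on the all-step score has 65–89%. The score has to cover all steps.

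**The case against.** The other side has real points.

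- **The wording is mixed.** The comparison sentence speaks of means, so the text does not plainly order a cut before the locks are compared. That stands as a description. But the test it names works only on counts, so no workable graded comparison is planned on either reading.
- **Graded information is partly kept.** Each step's average is reported. True, but it is set against 3 and not tested between locks.
- **The size is assumed.** The scale, baseline, correlation, effect and significance level are all unstated. A reader might infer a fixed 20-to-40-point loss, or that established heparin users rate heparin near the top of the scale. The documents give no ratings and support neither.
- **It is a pilot.** A reader might infer that the trial's main conclusion is unsafe. It is not: the primary objective is acceptability, ease of use is not among the listed secondary aims, and the 75% rule concerns willingness to continue. As a pilot summary, a proportion is readable and matches items 1 and 2.
- **Comparing only shared steps looks fairer.** It can hide the very burden EDTA adds, and can then do worse than the present plan.

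What remains is that the Protocol itself plans tests for any difference between locks, and names for that purpose a test that leaves out most of the collected grading.

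**Conclusion.** The concern holds in a limited form. The Protocol collects a graded, paired ease score and then compares locks with a test that can use only its dichotomised version, in a sentence that also calls the compared quantities means. For moderate effects, with 20 pairs, two-sided 0.05, five-point items and a cut near 4, the loss of power is typically about 20 to 40 points even with correct pairing. It is smaller, with medians of about 9 to 17 points, where the score analysis itself has very low or very high power. Near a ceiling or with high within-patient correlation it can be larger. Dropouts would reduce the number of pairs. The consequence is an inefficient comparison of a non-primary outcome in a pilot that makes no power claim.

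**What to change.** In the Protocol's Statistical analysis section, item 3 and the comparison paragraph:

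1. Make the quantity compared between locks the within-patient difference in mean ease score, each mean taken over all steps that lock procedure requires, including drawing up and withdrawing where they apply.
2. Report that difference with a 95% confidence interval and a Wilcoxon signed-rank test, in place of the chi-squared test for this outcome.
3. Report the difference over common steps only as a supportive analysis.
4. Keep the proportion 'easy or very easy' per lock and the per-step averages as descriptive figures.

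The cost is a change of wording. The same Form 2 answers serve, with no extra patients, calls or data. There are two small downsides. A score difference is less readable than a percentage, which the retained proportion covers. The all-step means also average over different numbers of items for different locks, which the supportive common-steps analysis and the per-step averages make visible.
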